11.2.5 Pharmacokinetic Analyses

As a primary endpoint in Part 1 and Part 3 of the study, PK parameters will be determined using noncompartmental methods. AUC from Time 0 to the last observation will be calculated using the trapezoid rule. The k_{el} will be calculated using log-linear regression on the terminal part of the concentration time curve. The terminal half-life and the AUC from the last observation to infinity will be calculated from the estimated k_{el} . Other parameters to be determined are C_{max} , T_{max} , V_{ss}/F , and Cl/F .

As a secondary endpoint, the effect of food on PK parameters including, but not limited to, C_{max} and AUC, will be compared using linear mixed effect model.

11.2.6 Exploratory Analysis - Relationship Between PK and QTc

As an exploratory endpoint of the study, the relationship between the concentration of oral rucaparib (PK) and potential changes in QTc will be studied. A linear and nonlinear mixed effect modeling approach will be used to quantify the relationship between the plasma concentration and the $\Delta\Delta QTc$ (time-matched, on-treatment to pretreatment difference in QTc interval, baseline-adjusted). Plots of the mean QT/QTc versus drug concentrations and a concentration-QT variables correlation will be explored.

11.2.7 Exploratory Analysis - Metabolite Profiling at the Recommended Phase 2 Dose

As an exploratory endpoint of the study, additional plasma samples will be collected on Day 15 from three patients enrolled in the RP2D Expansion cohort. Individual pooled plasma samples, one from each of these patients, will be prepared using the method proposed by Hamilton.⁷ The pooled plasma samples will be further processed before being analyzed by high-performance liquid chromatography coupled in-line with ultraviolet spectrophotometric and tandem mass spectrometric detection (HPLC-UV-MS/MS).

11.2.8 Safety Analyses

The safety analyses will be performed using the safety population (all patients who have received at least one dose of rucaparib).

11.2.8.1 Extent of Exposure

The following will be summarized by study part (i.e., Part 1, 2, and 3) and by dose group using descriptive statistics:

- Number of patients receiving at least one dose
- Number of patients at each dose group, average dose amount
- Number of cycles initiated
- Number of dose reductions/delays

- Number of dose interruptions

The number of patients at each dose group will be summarized with frequencies and percentages; the average dose will be summarized with descriptive statistics and frequency counts for relevant categories. The number of cycles initiated will be investigated by summarizing the number of cycles started by each patient in each period. The number of patients with at least one dose reduction/delay or interruption will be summarized with frequencies and percentages.

11.2.8.2 Adverse Events

The safety analyses will be performed using the safety population for each part of the study separately.

AE coding will be performed using the Medical Dictionary for Drug Regulatory Activities. The severity of the toxicities will be graded according to the NCI CTCAE whenever possible. Treatment-emergent AEs are defined as AEs with an onset date on or after the date of first dose of rucaparib until the date of the last rucaparib dose plus 28 days. AEs will be considered treatment-emergent if all or part of the date of onset of the AE is missing and it cannot be determined if the AE meets the definition for treatment-emergent.

The number and percentage of patients who experienced treatment-emergent AEs for each system organ class and preferred term will be presented by dose group. Multiple instances of the treatment-emergent AEs in each system organ class and multiple occurrences of the same preferred term are counted only once per patient. The number and percentage of patients with at least one treatment-emergent AE will also be summarized by dose group.

Separate tables will present the following by dose group:

- All treatment-emergent AEs
- Treatment-emergent AEs by CTCAE grade
- Grade 3 or greater treatment-emergent AEs
- Treatment-related, treatment-emergent AEs
- Dose-limiting toxicity AEs
- Serious treatment-emergent AEs
- Treatment-emergent AEs with an outcome of death
- Treatment-emergent AEs leading to discontinuation of oral rucaparib
- Treatment-emergent AEs resulting in interruption or reduction/delay of rucaparib

The incidence of treatment-emergent AEs will be summarized by relationship to oral rucaparib using “treatment-related” and “not treatment-related” categories. The category of treatment-related is defined as a relationship of Possible/Probable, Definite, or Missing. If a patient experiences multiple occurrences of the same AE with different relationship categories, the patient will be counted once as a relationship category of treatment-related.

If a patient experiences multiple occurrences of the same AE with different intensity toxicity grades, the patient will be counted once for the maximum (most severe) toxicity grade. AEs with a missing intensity will be presented in the summary table with a toxicity grade of “Missing.” For each toxicity grade, the number and percentage of patients with at least one treatment-emergent AE of the given grade will be summarized.

Non-treatment-emergent AEs (pretreatment and post-treatment) will be presented in the by-patient data listings.

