5.1.5 End-of-Treatment and Follow-Up (Part 1, Part 2, and Part 3)

All patients should return to the clinic for end-of-treatment assessments upon discontinuation of rucaparib and for follow-up of AEs at 28 (± 3) days after the last dose of oral rucaparib has been administered. During Parts 1 to 3, AEs will be assessed from the time of informed consent through 28 days after the last dose. Part 2B patients will be followed for survival, subsequent treatments, and secondary malignancy monitoring every 12 weeks [± 7 days].

[figure not shown]

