- ^f = Includes hemoglobin, hematocrit, WBC and differential (with ANC), and platelet count. Blood will be analyzed by a local laboratory and must be reviewed by the investigator prior to dosing with rucaparib.
- ^g = To be performed ≤ 14 days prior to the first dose of rucaparib.
- ^h = Includes total protein, albumin, creatinine, BUN or urea, total bilirubin, ALP, ALT, AST, total cholesterol, glucose, sodium, potassium, chloride, CO₂, calcium, and phosphorus. Blood will be analyzed by a local laboratory.
- ⁱ = Serum β -hCG (evaluated by local laboratory) will be performed only on women of childbearing potential at the following time points: ≤ 3 days prior to the first dose of rucaparib, ≤ 3 days prior to Day 1 of every cycle from Cycle 2 and beyond, and at the End-of-Treatment Visit.
- ^j = CA-125 as measured by a local laboratory.
- ^k = Includes dipstick for protein, glucose, blood, pH, and ketones. If dipstick findings are abnormal, then a microscopic evaluation will be performed to assess the abnormal findings.
- ^l = Tumor assessments to consist of clinical examination and appropriate imaging techniques (preferably CT scans of the chest, abdomen, and pelvis, with appropriate slice thickness per RECIST); other studies (MRI, X-ray, PET, and ultrasound) may be performed if required. The same methods used to detect lesions at baseline are to be used to follow the same lesions throughout the clinical study. Tumor scans will be collected and sent for evaluation by independent radiology review.
- ^m = Tumor scans to be performed within 7 days prior to the start of Cycles 3, 5, and 7, and then within 7 days prior to the start of every third cycle of treatment thereafter, beginning at Cycle 10. If initial CR or PR is noted prior to start of Cycle 7 or beyond, confirmatory scans must be performed 4–6 weeks later.
- ⁿ = A mandatory archival tumor biopsy will be collected from newly enrolled patients and from previously enrolled patients who provide additional consent. Refer to the Pathology Charter for detailed sample handling instructions. May be collected at Any time during study.
- ^o = AEs are recorded from time of signing of informed consent through 28 days after last dose of rucaparib. Ongoing SAEs should be followed until resolution.
- ^p = PK sample to be collected approximately 12 h after the last dose, but prior to the next dose (i.e., typically 5–10 min prior to dosing).

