9.10.4 Safety Evaluations

9.10.4.1 Adverse Event Assessment

The investigator has the responsibility for assessing the safety of the patients and for compliance with the protocol to ensure study integrity. Patients will be monitored for AEs during study participation (beginning at the time informed consent is obtained) and until 28 days after the last dose of oral rucaparib. Any ongoing SAEs will be followed until resolution or stabilization. AEs and laboratory abnormalities will be graded according to the NCI CTCAE² grading system and recorded on the eCRF.

Complete details for monitoring AEs, including the definition of drug-related AEs, are provided in [Section 10](#).

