10.6 Pregnancy or Drug Exposure During Pregnancy

Patients should be instructed to notify the investigator if pregnancy is discovered either during or within 6 months of completing treatment with rucaparib. This also applies to male patients whose partners become pregnant in the same timeframe. Women who become pregnant during the study will discontinue rucaparib immediately and the event will be reported on a specific Pregnancy Report Form in the same reporting timeframe as an SAE (Section 10.9). The pregnancy will be followed to term, any premature terminations or obstetric complications reported, and the status of mother and child will be reported to the sponsor as soon as possible after delivery.

10.7 Recording of Adverse Events, Serious Adverse Events, and Adverse Events of Special Interest

Any AE that occurs after the first dose of study drug to 28 days after receiving the last dose of oral rucaparib will be recorded on the AE eCRF. In addition, any AE/SAE that occurs after informed consent is obtained and is deemed related to a screening procedure for the study should also be reported. In order to avoid vague, ambiguous, or colloquial expressions, the AE should be recorded in standard medical terminology rather than the patient's own words. Whenever possible, the investigator should combine signs and symptoms that constitute a single disease entity or syndrome. For example, fever, headache, and nasal discharge may be reported as coryza, if that is a reasonable diagnosis.

The existence of an AE may be concluded from a spontaneous report of the patient; from the physical examination; or from special tests such as the ECG, laboratory assessments, or other study-specified procedure (source of AE).

Each AE is to be evaluated for duration, severity, seriousness, and causal relationship to the investigational drug. The action taken and the outcome must also be recorded.

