### 14.1 Adverse Events

Adverse events will be classified using the Medical Dictionary for Drug Regulatory Activities (MedDRA) classification system with version 19.1 or higher. The severity of the toxicities will be graded according to the NCI CTCAE v.4.03 or higher. Treatment-emergent adverse events (TEAEs) are defined as AEs with onset date on or after the date of first dose of study medication until the date of the last study medication dose plus 28 days. Adverse events will be considered treatment-emergent if all or part of the date of onset of the adverse event is missing and it cannot be determined if the adverse event meets the definition for treatment-emergent.

The number and percentage of patients who experienced TEAEs for each system organ class and preferred term will be presented. Multiple instances of the TEAE in each system organ class and multiple occurrences of the same preferred term are counted only once per patient. The number and percentage of patients with at least one TEAE will also be summarized.

Separate tables will be presented as follows:

- All TEAEs;
- TEAEs by CTCAE grade;
- Grade 3 or greater TEAEs;
- Treatment-related TEAEs;
- Serious TEAEs;
- Serious treatment-related TEAEs;
- TEAEs with an outcome of death;
- TEAEs leading to discontinuation of rucaparib;
- TEAEs resulting in interruption of rucaparib; and
- TEAEs resulting in reduction of rucaparib
- TEAEs resulting in reduction/interruption of rucaparib.
- Time to the first TEAE that results in a reduction, delay, interruption or discontinuation of rucaparib; and
- Time to the first treatment-related TEAE that results in a reduction, delay, interruption or discontinuation of rucaparib.

The incidence of TEAEs will be summarized by relationship to study drug according to the following categories: “treatment-related,” or “not treatment-related”. The category of treatment-related is defined as a relationship of “Possible/Probable”, “Definitely”, or missing. If a patient experiences multiple occurrences of the same AE with different relationship categories, the patient will be counted once as a relationship category of treatment related.

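### TEAEs are defined by onset date alone and no rule dates a worsening, so a screening-period symptom that worsens on rucaparib can drop out of every TEAE table

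*Protocol*

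**What the plan says.** **Definition.** Protocol 11.2.8.2: "Treatment-emergent AEs are defined as AEs with an onset date on or after the date of first dose of rucaparib", ending 28 days after the last dose. SAP 14.1: "Treatment-emergent adverse events (TEAEs) are defined as AEs with onset date on or after the date of first dose of study medication", with the same end. The only exception in either document concerns missing dates. In the protocol's words, "AEs will be considered treatment-emergent if all or part of the date of onset of the AE is missing", provided the status cannot otherwise be determined.

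**What happens to other events.** Protocol 11.2.8.2: "Non-treatment-emergent AEs (pretreatment and post-treatment) will be presented in the by-patient data listings". SAP 14.1 also sends non-TEAEs to a listing.

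**When recording starts.** The footnotes to the schedules of assessments (Tables 9, 10, 11 and 13) say: "AEs are recorded from time of signing of informed consent through 28 days after last dose of rucaparib". Section 5.1.5 agrees: "During Parts 1 to 3, AEs will be assessed from the time of informed consent through 28 days after the last dose". So do 9.10.4.1 and the end-of-treatment paragraph of the synopsis. Section 10.7 starts later: "Any AE that occurs after the first dose of study drug to 28 days after receiving the last dose of oral rucaparib" goes on the AE eCRF, and the only pre-dose events it adds are those judged related to a screening procedure. Section 5.1.1 and the opening of the synopsis study design likewise name only procedure-related events before first dose.

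**Worsening.** Protocol 10.1 includes an exacerbation of a pre-existing condition or event in the definition of an AE. Neither document says whether a grade increase opens a new record or is entered on the existing one.

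**The concern.** AE incidence is a secondary endpoint in all three parts. The TEAE definition feeds the tables for all events, Grade 3 or higher, related, serious and fatal events, and those leading to discontinuation, interruption or reduction. It also feeds the SAP's time-to-first-event analyses. An onset-only rule works if every on-drug worsening has its own dated record. If it does not, a symptom that starts mild in screening and becomes severe on drug keeps its pre-dose onset date and is not counted at any grade.

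Symptoms are the exposed group. Protocol 3.2.2.1 lists nausea, vomiting, abdominal pain, decreased appetite and fatigue/asthenia among the treatment-related events seen in at least 15% of patients, and such symptoms can also arise from advanced ovarian cancer before dosing. Laboratory worsening has a second route into the report through the baseline-to-worst-grade shift tables in SAP 14.2. Symptoms have none.

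**Working it through.** The plan gives no figure on this point, so the check is a comparison of texts followed by a scale calculation.

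**1. Length of the exposed window.** Section 5.1.1 allows 30 days of screening before first dose. Part 3 screening runs from Day -37 to Day -7 (Table 13), but its first rucaparib dose is given on Day -7 (9.6 and 9.6.1): 37 - 7 = 30 days. The window is up to 30 days in every part.

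**2. One clinical course, three recording routes.** Take Grade 1 nausea that begins in screening, is unrelated to any study procedure, and reaches Grade 3 on rucaparib.

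- Route A: the site records from consent, as the schedules say, and later raises the grade on the same record. Onset is before first dose, so the event fails 11.2.8.2 and SAP 14.1 and appears only in a listing.
- Route B: the site records from consent and enters the worsening as a new AE, which 10.1 permits. The new onset is after first dose, so it is a TEAE.
- Route C: the site follows 10.7. Nothing is recorded before dosing, and the exacerbation is first entered on treatment. Dated at the exacerbation, it is a TEAE.

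Only Route A omits the event, and it needs two conditions together: a record opened from consent, and the later grade entered on that record. For a procedure-related screening event, 10.7 also opens a pre-dose record, so for those events the outcome depends on the second condition alone.

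**3. Does another rule rescue Route A?** The missing-date rule does not, because the onset date is known. The maximum-grade rule does not, because it ranks grades within events already classed as treatment-emergent. The shift tables do not, because they cover laboratory parameters only.

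**4. Scale.** The planned sizes are 41 (Part 2A), 40 (Part 2B) and about 20 (Part 3), from protocol 6.1 and 11.4. The change in an incidence per omitted patient is 1/n:

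- Part 2A: 1/41 = 2.4 percentage points
- Part 2B: 1/40 = 2.5 percentage points
- Part 3: 1/20 = 5 percentage points

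The mechanism only removes events, so the direction is downward. The documents give nothing from which to estimate how many patients would follow Route A.

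**The case against.** The strongest reply is that 10.1 already closes the gap: an exacerbation is an AE, it begins on drug, and its onset satisfies the TEAE rule. On that reading the conflict over recording start decides nothing, and what matters is eCRF practice. Section 13.5 places full eCRF instructions in the investigator files, which are not among these documents and may contain the missing rule. This largely stands. A reader might infer that a site's choice between the schedules and 10.7 settles the matter alone; it does not, because Route B follows the schedules and still counts the event. But 10.1 says what an AE is, not how its onset is dated, and the counting rule in both documents depends on that date. Counting under Route C is likewise an inference, since 10.7 does not say which date to enter.

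A second reply concerns reach. Exclusion criterion 6 admits patients with ongoing Grade 1 toxicity from prior treatment, and Grade 2 non-hematologic toxicity with sponsor approval. A reader might infer that worsening of all such toxicity is at risk. The documents do not support that: it would generally have begun before consent, so neither recording rule would give it a pre-dose AE record. The exposed events are those that start between consent and first dose.

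Third, the consequences are bounded. Omitted events stay in listings, SAEs are reportable from consent under 10.7, and DLTs are defined by occurrence in Cycle 1 (7.4.1.4), not by TEAE status. The Grade 3/4 treatment-related events above 5% in 3.2.2.1 are anemia/decreased hemoglobin and increased ALT, which the shift tables cover. The safety tables are descriptive, with no comparison between treatment arms. All of this is correct and limits the point to symptom incidence.

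**Conclusion.** The point holds in a narrow form. Both documents define TEAEs by onset alone, the protocol gives two starting points for AE recording, and neither document dates a worsening. A non-laboratory event that starts in the screening window, is recorded from consent and is updated on the same record is left out of every TEAE table, while the same course entered as a new record, or first entered under 10.7, is counted.

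The effect is a downward bias in symptom incidence of about 2.4, 2.5 or 5 points per omitted patient in Parts 2A, 2B and 3, taking the safety population to equal the planned size. A reader might want an expected number of affected patients, or might infer that safety is materially under-reported. The documents support neither, because they give no frequency of screening-onset symptoms, of worsening, or of same-record updating. The conclusion also assumes that the eCRF instructions do not already require a separate record. The change is worth making because it removes an ambiguity in a counting rule at almost no cost, not because the study's safety conclusions are shown to be wrong.

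**What to change.** 1. In protocol 11.2.8.2 and SAP 14.1, define a TEAE as an AE with onset, or a pre-dose event with an increase in CTCAE grade, on or after first dose and through 28 days after the last dose.
2. State that such a worsening is entered as a new eCRF record dated at the grade increase, consistent with 10.1.
3. Reconcile the synopsis, 5.1.1, 5.1.5, the footnotes to Tables 9, 10, 11 and 13, 9.10.4.1 and 10.7 to one AE recording start. Which start to use is a design choice, but it should not be changed without item 1: moving 10.7 to consent alone would place more events on the route that omits them.

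The cost is a few sentences in each document and an eCRF completion note. Reported TEAE rates may rise slightly. Where data are already collected, records with a pre-dose onset and a later on-treatment grade increase would need review, as far as the eCRF kept the date of the change.

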11.2.8.3 Clinical Laboratory Evaluations

The clinical laboratory evaluations will be summarized using the safety population for each part of the study separately.

Clinical laboratory evaluations include the continuous variables for hematology, serum chemistry, and urinalysis. Laboratory values will be presented in Systeme International units. The baseline laboratory value will be defined as the last value prior to or on the day of the first dose of oral rucaparib. The on-treatment period will be defined as the day after the first dose of oral rucaparib to 28 days after the last dose of rucaparib. Laboratory values collected during the on-treatment period will be included in the summary tables. The laboratory values collected after the on-treatment period will only be presented in the data listings.

The summary of laboratory data will include descriptive statistics (N, mean, standard deviation, minimum, median, and maximum) of the maximum, minimum, and last value during the treatment period by dose group. Summaries using descriptive statistics of the change from baseline to the maximum, minimum, and last value during the on-treatment period will also be given by dose group. Supporting laboratory data including normal ranges and abnormal laboratory flags will be provided using by-patient listings. Separate listings will be produced for clinically significant laboratory abnormalities (i.e., those that meet Grade 3 or 4 criteria according to CTCAE) by dose group.

11.2.8.4 Vital Sign Measurements

The vital signs measurements will be summarized using the safety population for each part of the study separately.

The baseline vital sign measurement will be defined as the last value prior to or on the day of the first dose of rucaparib. The on-treatment period will be defined as the day after the first dose of rucaparib to 28 days after the last dose of rucaparib. Vital sign measurements collected during the on-treatment period will be included in the summary tables. The vital sign measurements collected after the on-treatment period will only be presented in the data listings.

The summary of vital sign data will include descriptive statistics (N, mean, standard deviation, minimum, median, and maximum) of the maximum, minimum, and last value during the on-treatment period by dose group. Summaries using descriptive statistics of the change from baseline to the maximum, minimum, and last value during the on-treatment period will also be given by dose group.

11.2.8.5 12-Lead Electrocardiograms

From ECGs conducted in Part 1 of the study, ECG intervals will be stratified into categories indicative of potential clinical significance. Each patient's maximum QT and QTc intervals from the pretreatment visit and treatment period visits will be classified as ≤ 450 msec, >450 to ≤ 480 msec, >480 to ≤ 500 msec, and >500 msec. For each patient's maximum change from the pretreatment ECG visit for QT and QTc, intervals will be classified into <30 msec, ≥ 30 to <60 msec, and ≥ 60 msec. The number and percentage of patients in each classified category will be presented. Additional endpoints will include abnormal T waves and U waves and other ECG intervals and diagnostic parameters.

Descriptive statistics will be used to summarize other ECG parameters of PR, QRS, QT, and RR interval, and the corresponding changes from pretreatment ECG visit at each time point. Plots of the mean QT/QTc over time for Day 1 and Day 15 of Cycle 1/pretreatment ECG day measurements will be provided.

